3.3 Secondary Objectives

The secondary efficacy objective is:

- To compare secondary efficacy/safety endpoints to one-year between randomised BIS target groups 50 and 35.

The secondary endpoints are:

1. **MI:** According to the 3rd Universal Definition (Thygesen K, Alpert JS, Jaffe AS, et al. Third universal definition of myocardial infarction. Circulation 2012;126:2020-35.), defined by either of:
 - A typical rise of troponin OR a typical fall of an elevated troponin OR a rapid rise and fall of CK-MB, PLUS one of the following: i) ischaemic symptoms, ii) pathological Q waves, iii) ECG changes indicative of ischaemia, iv) coronary artery intervention, and/or v) new or presumed new wall motion abnormality on echo or mibi scan; OR
 - Autopsy findings of MI
2. **Cardiac arrest:** Defined as a successful resuscitation from either documented or presumed ventricular fibrillation or sustained ventricular tachycardia or asystole
3. **Pulmonary embolism:** high probability VQ scan or documented on pulmonary angiogram or spiral CT, or at autopsy
4. **Stroke:** cerebral infarction or haemorrhage on CT or MRI scan, or new neurological signs (paralysis, weakness or speech difficulties) lasting more than 24 hours or leading to earlier death
5. **Sepsis:** using Centers for Disease Control and Prevention with National Healthcare Safety Network criteria: - SIRS plus infection (positive blood culture or purulence from any site)
6. **Surgical site infection:** if associated with purulent discharge and/or a positive microbial culture
7. **MI, cardiac arrest, PE and stroke:** the composite of secondary cardiac endpoints 1 to 4.
8. **Total ICU stay:** including initial ICU admission and readmission time
9. **Hospital stay:** from the start (date, time) of surgery until actual hospital discharge.

10. **Awareness:** Questioning for evidence of awareness under anaesthetic using the modified Brice questionnaire administered once in hospital, preferably on the day following surgery, and again on day 30.
11. **WHODAS score:** pre-operative, day 30 and 1 year
12. **Disability free survival:** disability-free survival up to 1 year: survival and freedom from new-onset disability, the latter defined as a 4-point or greater increase in the WHODAS score. Disability will be assessed by the participant, but if unable then we will use the proxy's report. The date of onset of new disability will be recorded.

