4.2 Sample size calculation

One year all-cause mortality is expected to be ~10% based on the findings of Leslie et al. and Gurman et al. The relative risk reduction in mortality in the BIS=50 group is expected to be 20%. A power analysis using $p_1=0.10$ and $p_2=0.08$ indicates that $N=3250$ patients are required in each group, $1-\beta=0.8$, $\alpha=0.049$. The alpha level is reduced to allow for the single interim analysis.

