8 EFFICACY ANALYSES

8.1 Primary endpoint analyses:

The primary endpoint analysis will compare the primary endpoint, one-year mortality in the intention-to-treat population, using a Mantel-Haenszel Chi-square test, stratified by study-centre groups. The pooled estimate of the odds ratio and 95% confidence interval from this analysis will be used to summarise the statistical comparison.

Supportive analysis of the primary endpoint will compare randomised groups using a stratified log-rank test with results summarised using Kaplan-Meier curves and hazard ratios in which withdrawn participants will be censored at the last date that they are confirmed to be event-free.

A two-tailed p-value < 0.049 will be taken to indicate statistical significance. The primary endpoint will be analysed using the full analysis set i.e. using those individuals who have confirmed outcome status, with groups designated as randomised on the intention-to-treat basis. Sensitivity analyses will also be undertaken with those missing outcome data assigned a poor outcome.

8.2 Secondary efficacy analyses:

The differences between randomised groups will be analysed using stratified Mantel-Haenszel Chi-square tests, stratified by study-centre group and general linear models, as appropriate to the form of the secondary endpoint. The occurrence of MI, cardiac arrest, PE, stroke, cardiac composite, surgical site infection, sepsis, infection composite, awareness, persistent post-operative pain and cancer recurrence within one year post-surgery will be analysed using stratified Mantel-Haenszel Chi-square tests. Supportive analysis of these secondary endpoints will compare randomised groups using a stratified log-rank test with results summarised using Kaplan-Meier curves in which withdrawn participants will be censored at the last date they are confirmed to be event-free. Sensitivity analyses will also be undertaken for these secondary endpoints with those missing outcome data assigned a poor outcome.

ICU stay, hospital stay, days disability-free and alive within one-year post-surgery and WHODAS scores at 30 days and 1 year will be analysed using general linear models with study-centre group and randomised treatment as

fixed factors. If the data do not meet assumptions for parametric analyses, the data will be log-transformed and if this does not achieve adequate normality then the groups will be compared using the Mann-Whitney U non-parametric tests.

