The endpoints; infection composite (the composite of secondary endpoints sepsis, surgical site infection) and composite of mortality and cardiac events (mortality MI, cardiac arrest, PE and stroke) will be compared between randomised groups using stratified Mantel-Haenszel Chi-square tests and using a stratified log-rank test with results summarised using Kaplan-Meier curves in which withdrawn participants will be censored at the last date they are confirmed to be event-free.

Standard descriptive statistics including frequencies, percentages, means, medians and ranges will be used to describe the levels for the secondary endpoints. The differences between randomised groups for the secondary endpoints will be summarised using model derived odds ratios and mean differences with 95% confidence intervals.

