12 MISSING DATA

In the event that a patient withdraws (discontinues the study or is lost to follow-up) from the study, information on their survival and secondary endpoint status at the time they are withdrawn will be included in the relevant endpoint analysis. Sensitivity analyses will also be undertaken with those missing outcome event data will be assigned a poor outcome. There will be no imputation of the ICU stay, hospital stay, days disability-free and alive within one-year post-surgery and WHODAS data at 30 days and 1 year.

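### The normality-driven fallback for the continuous secondary endpoints probably ends, for ICU stay and disability-free days, at an unstratified rank test with no matching estimate; disability-free survival also lacks a censored time-to-event analysis

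*Combined protocol and SAP*

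**What the plan says.** - **Randomisation (section 4.1)** is stratified by centre-group. The number of centre-groups is not given.
- **Test sequence (section 8.2).** ICU stay, hospital stay, days disability-free and alive, and WHODAS scores start with a general linear model that has centre-group and treatment as fixed factors. If assumptions fail, the data are logged; "if this does not achieve adequate normality then the groups will be compared using the Mann-Whitney U non-parametric tests". No criterion for adequate normality is given, no rule for zeros, and no stratification for the rank test.
- **Effect measure (section 8.2).** Differences in secondary endpoints are to be "summarised using model derived odds ratios and mean differences with 95% confidence intervals".
- **Disability-free survival (section 3.3, item 12)** is survival without new disability up to one year, and "The date of onset of new disability will be recorded". Section 8.2 gives the event-type secondary endpoints a supportive stratified log-rank analysis with censoring at the last date confirmed event-free. Disability-free survival is not on that list.
- **Hospital stay (section 3.3, item 9)** runs from the start of surgery "until actual hospital discharge". In-hospital death is not mentioned.
- **Missing data (section 12).** "There will be no imputation of the ICU stay, hospital stay, days disability-free and alive within one-year post-surgery and WHODAS data". The same section includes a withdrawn patient's endpoint status at withdrawal in the relevant analysis.

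**The concern.** The plan carries centre-group through the Mantel-Haenszel tests, the log-rank tests and the linear model, but the last step of this sequence does not. Which test is used depends on a look at the distribution, and for two of the four outcome types the intermediate step cannot help. The analyst would then leave a centre-adjusted analysis for one that ignores the randomisation strata and yields no estimate of the promised kind.

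When allocation is balanced within strata and the strata differ in outcome, an unstratified test overstates its own variance. The cost is therefore power, not false positives. Section 8.2.1 applies Holm-Bonferroni across ten measures, so the smallest p-value faces 0.05/10 = 0.005, which leaves little power to give away.

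Separately, a day count needs a rule for incomplete follow-up and a length of stay needs a rule for death before discharge. Neither is stated. Mortality is the outcome expected to differ between arms, so the second gap is not neutral by construction.

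**Working it through.** **1. The plan's own figure.** Section 4.2: "A power analysis using $p_1=0.10$ and $p_2=0.08$ indicates that $N=3250$ patients are required in each group", with 80% power and alpha 0.049 (two-tailed, per section 8.1). With p̄ = 0.09,

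n = [z₁₋α/₂·√(2p̄(1−p̄)) + z₁₋β·√(p₁q₁ + p₂q₂)]² / (p₁−p₂)²
= [1.9686 × 0.4047 + 0.8416 × 0.4045]² / 0.02² = 1.1371² / 0.0004 ≈ 3233 per group.

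This reproduces 3250 (power at 3250: 80.2%). Total size is 2 × 3250 = 6500. The plan gives no distributions, centre effects or withdrawal rates for the secondary endpoints, so every input below is an assumption.

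**2. The log step.**
- ICU stay: section 3.3 defines total ICU time. If patients never admitted score zero (an inference from the definition), log(0) does not exist.
- Disability-free days: with 75% at 365 and 25% spread evenly over the year, skewness is −2.0 raw and −3.6 after log(x+1). With 9% deaths and 20% new disability it goes from −1.7 to −3.6. The log makes it worse.
- Hospital stay is strictly positive. If roughly log-normal, the sequence stops at the logged linear model with centre-group retained.

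**3. Cost of the unstratified rank test where it is likely to be reached.** Simulated power at two-sided 0.05, 6500 patients, 8 centre groups, 600 runs (Monte Carlo error about 2 points):

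| Endpoint | Between-centre logit SD | Mann-Whitney | van Elteren |
|---|---|---|---|
| ICU stay, about 60% zeros | 0 / 0.3 / 0.6 / 1.0 / 1.5 | 58 / 63 / 55 / 47 / 33% | 58 / 63 / 57 / 50 / 41% |
| Disability-free days, 25% events | 0 / 0.3 / 0.5 / 0.8 | 68 / 63 / 64 / 59% | 67 / 62 / 64 / 62% |

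Further runs gave losses of about 0–2 points up to SD 0.6 and 4–7 points at SD 1.0. The ICU row above shows 3 points at SD 1.0, which is compatible given the Monte Carlo error.

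**4. Hospital stay, if the log step were nevertheless judged inadequate.** Log-normal stay, within-centre log SD 0.8, 5% shorter stay, 10 centre groups, 1000 runs:

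| Between-centre log SD | Logged linear model | Mann-Whitney | van Elteren |
|---|---|---|---|
| 0 | 0.687 | 0.675 | 0.669 |
| 0.3 | 0.708 | 0.661 | 0.704 |
| 0.6 | 0.704 | 0.505 | 0.684 |

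At SD 0.6 the type I error is 0.018 for Mann-Whitney and 0.044 for van Elteren. A second set of inputs (8 groups, within-centre SD 0.7, between-centre SD 0.6) gave 53% against 73%, a loss of 20 points.

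**5. Is the first step invalid?** No. Null rejection rates of the untransformed centre-adjusted linear model at nominal 5% were 0.038–0.055 (log-normal stay), 0.061 (ICU stay, skewness about 7) and 0.046 (disability-free days), with Monte Carlo error about 0.7 points.

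**6. Withdrawn patients' days, if counted as complete.** Assume 25% events and withdrawal, each uniform over the year.
- Mean with full follow-up: 0.75 × 365 + 0.25 × 182.5 = 319.4 days.
- Mean observed days in a withdrawn patient: 0.75 × 182.5 + 0.25 × (365/3) = 167.3 days.
- Shortfall per withdrawn patient: 319.4 − 167.3 = 152.1 days.
- A 2-point imbalance gives 0.02 × 152.1 ≈ 3.0 spurious days. The standard error is 2.4–2.6 days, so a null comparison is rejected 21–24% of the time.
- A 3-point imbalance (5% against 2%) gives 0.03 × 152.1 ≈ 4.6 days. If every withdrawal falls at day 180 and would otherwise have reached day 365 event-free, it gives 0.03 × (365 − 180) ≈ 5.6 days.

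**The case against.** The strongest reply is that the damage is modest and partly hypothetical.

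- A reader might infer that the sequence fails on every stay endpoint and costs 10 to 20 points of power. The documents do not support that. Such figures come from log-normal stay, where the plan as written stops at the logged model and keeps centre-group. They apply only if that step is rejected and centres differ strongly.
- A reader might infer that the plan counts truncated follow-up as complete days. It does not say so. Barring imputation can equally mean leaving those patients out, in which case the artefact in step 6 does not arise. The text is ambiguous; it does not prescribe the biased reading.
- Days alive and disability-free is a legitimate measure and handles death, because days stop accruing. WHODAS is scheduled only pre-operatively, at day 30 and at 1 year, so many onset dates will be reported between assessments, which limits a Cox analysis too.
- Adding a constant before taking logs is a common patch for zeros, and a mean difference could still be reported from the linear model.

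Most of this stands and sets the size of the point. It does not remove it. The added constant is not in the plan and does nothing for left skew. A mean difference from a model the plan has set aside would not match the reported p-value. And the robustness of the linear model does not help while the plan tells the analyst to abandon it on non-normality.

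**Conclusion.** The point holds in limited form and concerns secondary endpoints only. ICU stay and disability-free days will probably end at a rank test that ignores the randomisation strata and lacks the promised estimate. That test errs on the conservative side. The likely loss is 0–2 power points with small to moderate centre differences and about 4–7 points with large ones, on assumed distributions and 8 assumed centre groups at a nominal 5% level. Hospital stay is affected in this way only if its log is judged non-normal.

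Disability-free survival has a time-to-event definition and a recorded onset date, but no censored analysis and no stated rule for partial days. The spurious difference of about 3 days per 2 points of withdrawal imbalance is conditional on one reading of the missing-data text.

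It might also be inferred that in-hospital deaths are scored as short, favourable stays. The plan does not say that either; the rule is simply absent, and no figure in the documents sizes the effect. Ranking such deaths worst would be a choice of estimand, not the correction of an error. The sample size and primary analysis are untouched.

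**What to change.** 1. Remove the normality-driven choice of test. For each continuous secondary endpoint name one analysis in advance: either a van Elteren test stratified by centre-group with a Hodges-Lehmann or bootstrap confidence interval, or the centre-adjusted linear model with a bootstrap interval for the mean difference. The second holds its level at this sample size and keeps the effect measure already promised. State that patients not admitted to ICU have a stay of zero, if that is the intention.
2. Add a centre-stratified log-rank/Cox analysis of disability-free survival, censored at the last date confirmed event-free. If a days measure is kept, use restricted mean days to 365, so that partial follow-up is treated as censored. Censoring removes the artefact in step 6 only if it is non-informative.
3. State how a death before discharge enters hospital stay, and name the estimand that follows from that choice.

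The cost is SAP wording and a little more analysis; the onset date is already to be recorded. With no centre effect, stratifying the rank test costs essentially nothing (0.675 against 0.669 in step 4). If the rank test is chosen, the mean difference in stay becomes a descriptive summary, and the effect-measure sentence in section 8.2 should be changed to match.

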8.2.1 Type I error Control for secondary efficacy analyses

The statistical testing of the secondary efficacy measures will utilize the Holm-Bonferroni method to protect the type I error rate at 5%. There are ten secondary efficacy measures including the two composite outcomes outlined above. If a composite measure shows a statistically significant difference between groups using the Holm-Bonferroni procedure then the constituents measures will be compared using the adjusted p-value to determine statistical significance.

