3.4 Exploratory Objectives

1. **Infection composite:** the composite of secondary endpoints 5 and 6 (sepsis, surgical site infection).
2. **Composite of mortality and cardiac events:** the composite of the primary endpoint (mortality) and MI, cardiac arrest, PE and stroke.

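### The Holm rule for secondary outcomes does not hold its stated 5% once a composite has a real effect, if constituents are tested at their composite's threshold; and the ten measures are not listed

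*Combined protocol and SAP*

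**What the plan says.** SAP section 8.2.1 states that secondary testing "will utilize the Holm-Bonferroni method to protect the type I error rate at 5" per cent. It gives the size of the family without listing it: "There are ten secondary efficacy measures including the two composite outcomes outlined above". Constituents of a composite are tested only if the composite is significant, and "then the constituents measures will be compared using the adjusted p-value to determine statistical significance". The term adjusted p-value is not defined, and no division among constituents is given.

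Section 8.2 names the outcomes in two groups. The binary group is "The occurrence of MI, cardiac arrest, PE, stroke, cardiac composite, surgical site infection, sepsis, infection composite, awareness, persistent post-operative pain and cancer recurrence". The continuous group is "ICU stay, hospital stay, days disability-free and alive within one-year post-surgery and WHODAS scores at 30 days and 1 year". Section 3.3 makes the cardiac composite secondary endpoint 7, "the composite of secondary cardiac endpoints 1 to 4". Section 3.4 places the infection composite, and the composite of mortality with cardiac events, under Exploratory Objectives. The last part of section 8.2, just before 8.2.1, then describes this pair: "infection composite (the composite of secondary endpoints sepsis, surgical site infection) and composite of mortality and cardiac events".

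**The concern.** Holm on ten measures holds 5% because, when a measure is rejected, its share of alpha passes to those still untested. Section 8.2.1 appears to use that share again. A rejected composite opens tests of its constituents at the composite's own level, and Holm carries on down the list as if nothing had been spent. A composite can be rejected because of one real component; the other components are then true nulls, each tested at the full composite level.

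What is at stake is the 5% claim for statements about individual components. A composite with a real effect is the setting in which such statements would be made.

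The second issue is identification. Because the ten are not listed, and the pair of composites just above 8.2.1 differs from the pair that the outcome count implies, the choice of composites carrying the error control could be settled after the data are seen.

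**Working it through.** **Inputs.** From the SAP: family of 10 and 5% (8.2.1); four cardiac constituents (3.3, items 1-4); two infection constituents (3.3, items 5-6); the outcome lists in 8.2. The reading tested is that each constituent is compared with the Holm threshold at which its composite was rejected.

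**1. Can ten be reproduced?** Section 8.2 has 11 binary + 5 continuous = 16 outcomes. Removing the six constituents gives 16 - 6 = 10, with WHODAS counted at two times and the cardiac and infection composites as the two. From section 3.3: 15 endpoints - adverse events = 14; - 6 constituents = 8; WHODAS twice = 9. The tenth has to be the infection composite, which 3.4 calls exploratory. A second route also gives ten: the same 8, with WHODAS once, plus the pair described just above 8.2.1. That family would contain three composites.

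**2. Holm on the ten alone.** First step 0.05/10 = 0.005. Sum 10 x 0.005 = 0.050; with independent tests 1 - 0.995^10 = 0.049. The stated 5% is reproduced.

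**3. Nothing differs.** A constituent is tested only after its composite has been falsely rejected, so an error has already been counted. Simulated error: 0.050.

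**4. One cardiac component differs.** The composite is rejected at 0.005. The nine remaining measures, all null, share the full 0.05, and three null constituents add 3 x 0.005:
- bound: 0.05 + 0.015 = 0.065
- if independent: 1 - (1 - 0.05/9)^9 x 0.995^3 = 0.063

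**5. One component of each composite differs.** The composites are rejected at 0.005 and 0.05/9 = 0.0056:
- cardiac first: 0.05 + 3 x 0.005 + 0.0056 = 0.071
- infection first: 0.05 + 0.005 + 3 x 0.0056 = 0.072

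**6. All ten measures differ, composites tested last.** Holm's last two levels are 0.025 and 0.05. With three null cardiac constituents, one null infection constituent and independence:
- cardiac last: 1 - 0.95^3 x 0.975 = 0.164 (bound 3 x 0.05 + 0.025 = 0.175)
- infection last: 1 - 0.975^3 x 0.95 = 0.119

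**7. Simulation of the rule.** 40,000 trials with 3250 per arm (section 4.2); Monte Carlo standard error about 0.001. The documents give no component rates, so these are assumptions: control rates of MI 4%, cardiac arrest, PE and stroke 1% each, surgical site infection (SSI) 8%, sepsis 6%; true effects on MI (to 1.5%) and SSI (to 4.5%); other endpoints independent. The last column is the range when the assumed effect sizes are varied.

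| What truly differs | Simulated error | Range |
|---|---|---|
| Nothing | 5.0% | 4.9-5.0% |
| MI only | 5.8% | 5.4-6.2% |
| MI and SSI | 6.3% | 5.4-6.9% |
| MI, SSI and five other measures | 8.0% | not varied |
| MI, SSI and all eight other measures | 12.9% | 6-16% |

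**The case against.** The best defence is that the rule does limit constituent testing: constituents are examined only after their composite is rejected, and at a Holm level rather than at 0.05. The undefined term might also have been meant as a further adjustment among constituents. Both points are fair. A reader might infer that constituents are tested with no correction at all, and the text does not support that. What is missing is a split among them and a rule against spending the same alpha twice. If a stricter rule was meant, the SAP needs to state it.

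Three other strong readings also fail.

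- **That ten matches no endpoint list.** It matches section 8.2 exactly (step 1). The mismatch is with the labels in 3.3 and 3.4 and with the cross-reference in 8.2.1.
- **That the error can reach 1 - 0.95^4 = 18.5%.** With the cardiac and infection composites this would need both to be tested at 0.05. Holm reaches 0.05 only at its last step, and the step before is 0.025. Nor can all six constituents be false positives when both composites truly differ: at least one of each must be real, which leaves at most 3 + 1 = 4 nulls.
- **That sepsis and SSI can be examined only through an exploratory composite.** Section 8.2 analyses both unconditionally and reports effect estimates with 95% confidence intervals. Only the multiplicity-adjusted significance claim depends on the composite.

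It can also be said that the excess in the less extreme cases is small and touches secondary outcomes only. That stands, and it sets the priority.

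**Conclusion.** The concern holds on the natural reading of the undefined term: the rule does not give strong control at the 5% that the SAP states. The excess is conditional on a composite having a real effect. It is about one percentage point, and at most 1.5 points, when one cardiac component differs. It is at most about 2.2 points when one component of each composite differs. The 16.4% figure is a limit that requires all ten measures to differ, the cardiac composite to be tested last and independent constituents; it is not an expectation. The simulated values rest on assumed event rates and effects; the bounds in steps 4 and 5 do not.

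The unlisted family and the conflicting pairs of composites are a separate defect of labelling, certain from the text whichever reading of the constituent rule is taken.

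A reader might infer that the trial's main conclusion is at risk. It is not: the mortality test in section 8.1 has its own 0.049 level and is untouched. This is a should-fix.

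**What to change.** Amend the SAP before database lock, as section 13 allows.

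**Identify the family.** List the ten: cardiac composite, infection composite, ICU stay, hospital stay, awareness, WHODAS at 30 days, WHODAS at 1 year, disability-free survival, persistent pain, cancer recurrence. Name the cardiac and infection composites as the two. Move the infection composite from 3.4 to 3.3 and keep mortality plus cardiac events exploratory.

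**Replace the undefined term with one of three rules.**
- (a) One Holm family of 16 that includes the six constituents. The first step is 0.05/16 = 0.003125; under the assumptions in the working, the simulated error is 4.5-4.7% in every scenario.
- (b) Test constituents by Holm within their composite's alpha, and release that alpha to other measures only after all its constituents are rejected. At the starting levels the total is 8 x 0.005 + 0.005 + 0.005 = 0.050. The retention is essential: Holm among constituents while the main sequence moves on still gives bounds of 0.05 + 0.005 = 5.5% (cardiac composite rejected first), 0.05 + 0.005 + 0.0056 = 6.1% (both composites rejected first) and 0.05 + 0.025 = 7.5% (all ten differing, composites last).
- (c) State that constituent tests lie outside the 5% claim and are descriptive.

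**Cost.** SAP wording, plus power under (a) or (b). Under (a), the first threshold for every measure falls from 0.005 to 0.003125. Under (b), the first constituent threshold becomes 0.005/4 = 0.00125 or 0.005/2 = 0.0025. A constituent with 80% power at 0.005 (2.807 + 0.842 = 3.649 standard errors) would have about 66% at 0.00125 (3.649 - 3.227 = 0.422) or 73% at 0.0025 (3.649 - 3.023 = 0.626). The other eight measures also face slightly stricter levels: after both composites are rejected, they start at 0.04/8 = 0.005 rather than 0.05/8 = 0.00625 until a branch is released. Option (c) costs no power but gives up error-controlled claims on components.
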